6.6 DOSAGE MODIFICATION

Intra-patient dose-escalation from 150 mg to 200 mg is allowed after Cycle 3 (*preferable at Cycle 4, or latest, Cycle 5*) for patients who have demonstrated adequate tolerability and are showing a lack of Hct control *and/or inadequately controlled leukocytosis and/or thrombocytosis* at end of Cycle 3 (Section 4.1.2). Patients with PD will not be permitted to dose-escalate and should come off the study. Consideration for dose-increase will be based on a review of patient data, including but not limited to, safety data, response assessments and laboratory data. All intra-patient dose-escalation decisions will be

made in consultation with the Investigator and Sponsor, including the Medical Monitor and Safety Science Leader.

In case of hematologic toxicity (i.e., anemia, thrombocytopenia and/or neutropenia), patients may need treatment interruptions and/or dose reductions (see Table 8).

Guidance for dose-reductions for AEs is described in Section 8.3.9. Furthermore, after one year of treatment (end of Cycle 13), a reduction of the idasanutlin dose to 100 mg for all subsequent cycles may occur for any patient that has not previously had a reduction to 100 mg for other reasons to generate data for longer term tolerability. This reduction will be based on communication between the Investigator and Sponsor. Treatment may be re-escalated back to the prior highest tolerated dose if Hct increases to $\geq 45\%$ and/or CHR response is lost ($WBC \geq 10 \times 10^9/L$ and PLT count $> 450 \times 10^9/L$) to achieve a hematologic response. Treatment *must* not be re-escalated if the patient has progressive disease (see Appendix 1).

A treatment break may also be exercised if sufficient clinical response (CHR/Hct control) is ongoing at end of Cycle 13 or in subsequent cycles. For these patients, unscheduled hematologic response assessments should occur every 28 days and unscheduled full response assessment (as defined on SoA as for Week 32) should occur every 84 days, if treatment holiday is prolonged. Treatment may resume if Hct increases to $\geq 45\%$ and/or CHR response is lost ($WBC \geq 10 \times 10^9/L$ and PLT count $> 450 \times 10^9/L$). Treatment will thereafter continue until 2 years post initial dose. Treatment should not be re-initiated if the patient has progressive disease. If subsequent scheduled efficacy assessment after re-escalation indicate a lack of Hct control ($\geq 45\%$) or NR by ELN 2009, treatment should be discontinued.

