
 • To evaluate the efficacy of idasanutlin monotherapy in all patients (with and without splenomegaly) by complete hematologic response 	
 • Complete hematologic response at Week 32 Complete hematologic response requires all of the following: 
 – Hct control (protocol-specified ineligibility for phlebotomy between Weeks 8–32 and ≤ 1 instance of phlebotomy eligibility between first dose and Week 8); – WBC count $\leq 10 \times 10^9/L$ at Week 32 assessment; AND – PLT count $\leq 400 \times 10^9/L$ at Week 32 assessment • Complete hematologic remission at response Cycle 11 Day 28 defined as patients with all of the following: 
 – Hct control defined as protocol specified ineligibility for phlebotomy between Week 32 assessment and Cycle 11 Day 28 – WBC count $\leq 10 \times 10^9/L$ at Cycle 11 Day 28 assessment; AND – PLT count $\leq 400 \times 10^9/L$ at Week 32 assessment – Duration of complete hematologic remission response with a durable

Objectives	Endpoints

 To evaluate the efficacy of idasanutlin monotherapy by using modified ELN hematologic response criteria (complete and partial response) in patients with baseline splenomegaly, patients without baseline splenomegaly and in all patients irrespective of spleen size 	
responder defined as a subject in remission at Week 32 and Cycle 11 Day 28, as defined above
 
 Response by using modified ELN hematologic response criteria: 
 Complete response Partial response NR Progressive disease - as defined by increased bone marrow fibrosis from baseline, and/or transformation to MF, MDS or acute leukemia Duration of response, including proportion of patients with durable response lasting at least 12 weeks (Cycle 11 Day 28) from Week 32 (Cycle 8 Day 28) (Hct control, CHR, ELN 2009 response and composite response, if applicable)

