 - Platelet (PLT) count $> 400 \times 10^9/L$ and white blood cell (WBC) count $> 10 \times 10^9/L$ after 3 months of HU.
 - Failure to reduce splenomegaly extending > 10 cm below the costal margin by $> 50\%$, as measured by palpation after 3 months of HU.
 - Intolerance to HU is defined as at least one of the following:
 - Absolute neutrophil count (ANC) $< 1.0 \times 10^9/L$.
 - PLT count $< 100 \times 10^9/L$ or hemoglobin < 100 g/L (i.e., 10 g/dL) at the lowest dose of HU required to achieve a response.
 - Presence of leg ulcers or other unacceptable HU-related non-hematologic toxicities (such as mucocutaneous manifestations, GI symptoms, pneumonitis, or fever at any dose of HU).

For patients previously exposed to ruxolitinib, inclusion requires the following in addition to previous treatment for myeloproliferative disorder with HU:

- *Therapy resistant PV after at least 6 months of treatment with ruxolitinib, defined by at least one of following:*
 - *Need for phlebotomy to achieve Hct $< 45\%$, at least two over 6 months*
 - *Uncontrolled leukocytosis (WBC count $> 10 \times 10^9/L$)*
 - *Uncontrolled thrombocytosis (PLT count $> 400 \times 10^9/L$)*
 - *Failure to achieve a $> 50\%$ reduction in palpable splenomegaly measuring > 5 cm from the left costal margin or failure to become non-palpable in palpable splenomegaly measuring 0–5 cm*
 - *Inadequately controlled disease-related symptoms (e.g., pruritus, headache, night sweats, excluding fatigue) after excluding other causes*
- *Ruxolitinib intolerance defined as at least one of following at lowest dose of ruxolitinib to achieve adequate response:*
 - *Cytopenia defined as one or more of the following:*
 - Neutropenia, ANC $< 1.0 \times 10^9/L$*
 - Thrombocytopenia, PLT count $< 100 \times 10^9/L$*
 - Anemia, hemoglobin < 10 g/dL*
 - *Life threatening infections deemed associated with ruxolitinib or other infections complications possibly associated with ruxolitinib (shingles, TB, hepatitis reactivation) at any time during study treatment*

- *Non-melanoma skin cancer (recurrence of or multiple) at any time during study treatment*
- 7. *Adverse events likely caused by ruxolitinib (assessment of attending physician) and that is of a severity that precludes further treatment with ruxolitinib (as per judgment of the attending physician and the patient)*
- 8. Eastern Cooperative Oncology Group (ECOG) performance status of 0 to 1.

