5.7.2.2 Complete Hematologic response (CHR)

Similarly to be evaluated on the 3 Rux naïve populations: without splenomegaly, with splenomegaly; and with and without splenomegaly.

Complete hematologic response (CHR) requires all of the following:

- Hct control (protocol-specified ineligibility for phlebotomy between Weeks 8–32 and ≤ 1 instance of phlebotomy eligibility between first dose and Week 8);
- WBC count ≤ 10 × 10⁹/L at Week 32 assessment; AND
- PLT count ≤ 400 × 10⁹/L at Week 32 Assessment

Response rate per Complete Hematologic Response
Intent-to-Treat Patients
Protocol: {base protocol}

	Ruxolitin b Naïve (N=xx)				Ruxolitin b Exposed (N=xx)				All Patients (N=xx)	
	With Splenomegaly (N=xx)		Without Splenomegaly (N=xx)		With Splenomegaly (N=xx)		Without Splenomegaly (N=xx)			
	Cycle 3 Day 28 (N=xx)	Cycle X Day XX (N=xx)	Cycle 3 Day 28 (N=xx)	Cycle X Day XX (N=xx)	Cycle 3 Day 28 (N=xx)	Cycle X Day XX (N=xx)	Cycle 3 Day 28 (N=xx)	Cycle X Day XX (N=xx)	Cycle 3 Day 28 (N=xx)	Cycle X Day XX (N=xx)
CHR	xx (xx.x%)	xx (xx.x%)	xx (xx.x%)	xx (xx.x%)	xx (xx.x%)	xx (xx.x%)	xx (xx.x%)	xx (xx.x%)	xx (xx.x%)	xx (xx.x%)
95% CI	(x.xx, x.xx)	(x.xx, x.xx)	(x.xx, x.xx)	(x.xx, x.xx)	(x.xx, x.xx)	(x.xx, x.xx)	(x.xx, x.xx)	(x.xx, x.xx)	(x.xx, x.xx)	(x.xx, x.xx)
Complete Response (CR)	xx (xx.x%)	xx (xx.x%)	xx (xx.x%)	xx (xx.x%)	xx (xx.x%)	xx (xx.x%)	xx (xx.x%)	xx (xx.x%)	xx (xx.x%)	xx (xx.x%)

Note: Time points as per the protocol assessment schedule.

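### Section 6.6 labels its re-escalation and restart trigger as loss of CHR, but the counts it gives (WBC ≥10 and PLT >450) miss many patients who have lost CHR (WBC >10 or PLT >400)

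*Protocol*

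**What the plan says.** All counts below are ×10⁹/L.

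- **Protocol Section 6.6, re-escalation.** From the end of Cycle 13 the dose may be cut to 100 mg. It may go back up to the highest dose the patient previously tolerated if hematocrit is at least 45% "and/or CHR response is lost ($WBC \geq 10 \times 10^9/L$ and PLT count $> 450 \times 10^9/L$) to achieve a hematologic response".
- **Protocol Section 6.6, treatment break.** "Treatment may resume if Hct increases to" 45% or more, "and/or CHR response is lost", followed by the same bracket.
- **Protocol Section 3, Table 3.** "Complete hematologic response requires all of the following": hematocrit control, WBC ≤10 and platelets ≤400. SAP Section 5.7.2.2 repeats the definition, ending with "PLT count ≤ 400 × 10⁹/L at Week 32 Assessment".
- **Other rules on the same counts.** The Cycle 3 escalation rule in Section 6.6 acts on "inadequately controlled leukocytosis and/or thrombocytosis". In Section 5.1, ruxolitinib resistance lists "Uncontrolled thrombocytosis (PLT count $> 400" as sufficient alone, and WBC >10 likewise. Hydroxyurea resistance in the same section requires platelets >400 and WBC >10 together.

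Neither document explains a platelet limit of 450 or describes a retreatment threshold distinct from CHR.

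**The concern.** A response that requires several conditions together is lost as soon as one of them fails. Section 6.6 instead requires both counts to be abnormal, and it sets the platelet limit 50 higher than the definition does. The bracket is the only number a site has for deciding whether the count route is open, so the label and the figures give different answers for the same patient.

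The consequence is a dosing one. A patient on a break with WBC 9 and platelets 900, hematocrit below 45%, has plainly lost CHR, but read literally the figures do not allow restart. Section 6.5.2 forbids hydroxyurea and other PV-directed therapy on study apart from phlebotomy, aspirin and supportive care, so no other cytoreduction is available. Section 8 rules out waivers. One site may follow the label and another the figures, and similar patients would then be dosed differently. The SAP's CHR table shell also runs by protocol visit, so later visits could be classified with a limit of 400 while dosing follows 450.

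**Working it through.** The plan reports no figure to reproduce here. The check is one of logic.

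**Inputs.** CHR count limits: WBC ≤10 and PLT ≤400 (Protocol Section 3, SAP Section 5.7.2.2). Written trigger: WBC ≥10 and PLT >450 (Protocol Section 6.6, twice). Hematocrit is held below 45% with hematocrit control kept, so that only the count route is in play.

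**Step 1: negate the definition.** not(WBC ≤10 and PLT ≤400) = WBC >10 or PLT >400.

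**Step 2: compare case by case.** *Limits only* means WBC >10 and PLT >400. *Connector only* means WBC ≥10 or PLT >450. *Both* means WBC >10 or PLT >400.

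| WBC/PLT | CHR on counts | As written | Limits only | Connector only | Both |
|---|---|---|---|---|---|
| 20/300 | lost | not met | not met | met | met |
| 9/900 | lost | not met | not met | met | met |
| 12/430 | lost | not met | met | met | met |
| 9/430 | lost | not met | not met | not met | met |
| 10/460 | lost | met | not met | met | met |
| 11/460 | lost | met | met | met | met |
| 10/400 | kept | not met | not met | met | not met |
| 10/350 | kept | not met | not met | met | not met |

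Only the last column agrees with the CHR column in every row.

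**Step 3: check that no other pair behaves differently.** Take WBC 2.0 to 40.0 by 0.1 (381 values) and PLT 100 to 1500 by 1 (1,401 values), which gives 381 × 1,401 = 533,781 pairs. The counts test the logic. They depend on the chosen ranges and say nothing about how often patients fall in each cell.

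- CHR kept: 81 × 301 = 24,381. CHR lost: 533,781 − 24,381 = 509,400.
- Written trigger met: 301 × 1,050 = 316,050. All of these have PLT >450, so all have lost CHR, and CHR kept with trigger met = 0.
- CHR lost but trigger not met: 509,400 − 316,050 = 193,350.
- Limits only: met at 300 × 1,100 = 330,000; mismatches 509,400 − 330,000 = 179,400.
- Connector only: 80 × 50 = 4,000 pairs missed (WBC <10, PLT 401 to 450) plus 1 × 301 = 301 wrongly flagged (WBC exactly 10, PLT ≤400); total 4,301.
- Both changed: 0 mismatches.

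The written trigger is therefore a strict subset of loss of CHR on counts, and neither half of the correction is enough alone.

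**The case against.** The best defense is that 450 with a two-lineage requirement is a deliberately tighter retreatment rule. The 100 mg reduction is there to collect longer-term tolerability data, and a stricter trigger keeps more patients on that dose. With the limits aligned to CHR, a single platelet count of 401 would make a patient eligible for the higher dose, and the drug's gastrointestinal and cytopenic effects rise with exposure. The protocol also joins the two counts with *and* in its hydroxyurea-resistance criterion. This cannot be excluded as the intent, but the text calls the rule loss of CHR and gives no such reason. The hydroxyurea criterion concerns eligibility and uses 400.

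Two further points stand as limits on the finding:

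- The whole trigger is not simply narrower than loss of CHR. Its hematocrit route opens at 45%, whereas hematocrit control within CHR fails only at ≥45% with a rise of at least 3% over baseline, or above 48%. A patient with baseline and current hematocrit of 46% can keep CHR and still qualify. The one-way statement therefore applies to the count bracket only.
- CHR is formally defined at Week 32 and Cycle 11 Day 28. Applying its count limits after Cycle 13 is an inference, though one that Section 6.6 makes itself by using the term.

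The effect is also contained. The rule is permissive, hematocrit ≥45% suffices alone, patients on the reduction still receive 100 mg, and those on a break have response checked every 28 days, with phlebotomy and aspirin allowed.

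**Conclusion.** The concern holds. The figures in Section 6.6 do not describe what their label says, in both connector and platelet limit, and the error appears in both the re-escalation and the restart rule. Read literally, it withholds the count route from patients who have lost CHR on one lineage at any severity, and from those with WBC >10 and platelets of 401 to 450. The Cycle 3 escalation rule in the same section shows that single-lineage failure is otherwise treated as a reason to act.

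How many patients this affects cannot be derived from the documents. The group is limited to those who had CHR, are on the optional reduction or a break after Cycle 13, and keep hematocrit below 45%. The Week 32 and Cycle 11 Day 28 endpoints come earlier and are unaffected. The conclusion assumes that the CHR count limits carry forward beyond Cycle 13, as the label implies. The point should be corrected because it sets a dosing decision, but it does not threaten the trial's main results.

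**What to change.** In both paragraphs of Section 6.6 replace the bracket with *WBC >10 × 10⁹/L and/or PLT >400 × 10⁹/L*, and leave hematocrit ≥45% as a separate route. Change the limits and the connector together. This aligns the count part only; the hematocrit route remains its own threshold.

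If the sponsor intends the narrower rule, keep the figures, name them a separate retreatment threshold, and delete the statement that CHR is lost.

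The cost is wording in two paragraphs. The first option makes somewhat more patients eligible for a higher dose or a restart, some on small platelet excursions. That remains discretionary under the existing wording, and the bar on patients with progressive disease stays in place.

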- 19 (-)3/(+)1 day window for Cycle 3 Day 28, Cycle 5 Day 28 and End of Cycle 8 (Week 32) and for every 3 cycles beyond. Must be prior to start of subsequent cycle. For the timepoint “End of Cycle 8” (Week 32), a patient experiencing a Dose Delay would perform the critical efficacy assessment(s) at whichever timepoint came first (Week 32 or End of Cycle 8) and performed assessment(s) would be recorded within the appropriate folder. In cases of dose delay where Week 32 occurs prior to the End of Cycle 8, any assessments performed at Week 32 would not need to be repeated at the End of Cycle 8.
- 20 Per modified 2009 ELN Criteria (see [Appendix 1](#)) for patients with splenomegaly at baseline. Solely Hct control for patients without splenomegaly at Baseline.
- 21 (-3) day window for COA; the questionnaires must be completed before the patient receives any information on disease status, prior to the performance of non-COA assessments, and prior to the administration of study treatment.
- 22 Hematology and Serum Chemistry need only be obtained once end of Cycles 3, 5, and 8, but pre-dose Cycles 4, 6, and 9 based on window in footnote 19. Ideally these Hematology and Serum Chemistry assessments will be done at the same time as all other Response assessments required at end of Cycles 3, 5, and 8.
- 23 COA questionnaires are only to be completed at Cycle 2 Day 1, not at Cycle 3 Day 1.

Table 2 Detailed Schedule of Activities

Cycle	Day	Hours Post Dose	ECG - 12 Lead	PK Sample ^a	PDy Serum MIC-1 ^a	Nucleic Acid Whole Blood ^{b, c}	Paxgene Whole Blood	Exploratory Biomarker PDy Flow Blood	TBNK Panel Flow Cytometry Blood	Cytokine Assay Plasma ^c	RBR DNA Optional ^d	RBR Serum Optional	
Cycle 1	Day 1	0 PreDose	x	x	x	x	x	x	x	x	x	x	
		1		x									
		2		x									
		4	x	x									
		6	x	x									
		10 ^e		x									
	Day 2	0/PreDose	x	x	x		x						
	Day 5	0 PreDose	x	x	x			x					
		1		x									
		2		x									
		4	x	x	x								
6		x	x	x									
10 ^e			x	x			x		x	x			
Cycle 2	Day 1	0 PreDose	x			x	x		x	x			
Cycle 3	Day 1	0 PreDose	x ^f			x							
		4	x ^f										
		6	x ^f										
	Day 2	24/PreDose	x ^f										
	Day 28 ^g	N/A				x				x			

Table 2 Detailed Schedule of Activities (cont.)

Cycle	Day	Hours Post Dose	ECG - 12 Lead	PK Sample ^a	PDy Serum MIC-1 ^a	Nucleic Acid Whole Blood ^{b, c}	Paxgene Whole Blood	Exploratory Biomarker PDy Flow Blood	TBNK Panel Flow Cytometry Blood	Cytokine Assay Plasma ^c	RBR DNA Optional ^d	RBR Serum Optional	

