4.1.4 Study cycles

A treatment cycle starts on the day of the first administration of study treatment and ends the day before the start of the next cycle. For example, cycle 1 will start at the first valid cycle 1 study drug administration and will end at the start date of the first cycle 2 dose minus 1 day. The last cycle ends when the treatment period ends.

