4.1.9 Visits

The visits according to schedule of assessment are labeled as ‘Cycle x Day y’ (‘Cycle 1 Day 1’, ‘Cycle 2 Day 1’ etc.). Assessments are assigned to visits using the visit labels in SDTMv. In general, all summary tables by visit include all scheduled assessments as per SoA.

In case of multiple assessments per visit with a scheduled visit label, the visit with worst values is taken into account, otherwise the last visit is taken into account.

Note, in the majority of the summaries no ‘Cycle 1 Day 1’ is displayed because this is labeled as baseline.

If a Visit becomes a baseline value, it is only displayed as baseline. E.g. if ‘Cycle 1 Day 1’ is the baseline, then only Baseline is displayed in the outputs, followed by the next visit. In listings the original SDTMv visit label is shown.

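### Responders on a treatment break after Cycle 13 have no scheduled visit label, so the SAP's late by-visit response rates are biased downward

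*Protocol*

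**What the plan says.** Protocol 6.6 opens the break only to patients in response: "A treatment break may also be exercised if sufficient clinical response (CHR/Hct control) is ongoing at end of Cycle 13 or in subsequent cycles". During the break, "unscheduled hematologic response assessments should occur every 28 days and unscheduled full response assessment", the latter every 84 days if the break is prolonged. On restarting, the same section says "Treatment may resume if Hct increases to" 45% or more, and/or CHR is lost.

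The SAP handles visits in two places. Section 4.1.9 states: "Assessments are assigned to visits using the visit labels in SDTMv", and "In general, all summary tables by visit include all scheduled assessments as per SoA". Section 4.1.4 defines cycles by dosing: "A treatment cycle starts on the day of the first administration of study treatment and ends the day before the start of the next cycle".

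The schedule of activities places late response visits on Day 28 of Cycles 11, 14, 17, 20 and 23, and gives that timing for the case without dose delays. The by-visit response shells in SAP 5.7.1 and 5.7.2 follow the protocol schedule. No SAP rule says where an assessment made during a break belongs.

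**The concern.** Being on a break depends on the outcome. Only a patient with ongoing CHR or Hct control can take one, and the assessments made during it are the ones without a scheduled label. If the late by-visit tables are built from scheduled labels alone, the records left out belong to responders by construction. A patient who later resumes dosing regains a Cycle 14 label only after Hct has risen or CHR has been lost.

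What is at stake is the descriptive picture of response in the second year. Response held without drug would be collected every 28 days, yet would not appear as response in the tables.

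**Working it through.** **Chain of rules.** Cycles last 28 days, so without delays the end of Cycle c falls at Week 4c. Cycle 8 ends at Week 32, Cycle 11 at Week 44, Cycle 13 at Week 52, and Cycles 14, 17, 20 and 23 at Weeks 56, 68, 80 and 92.

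- Protocol 6.6: a break can start at Week 52 at the earliest, and its assessments are unscheduled.
- SAP 4.1.4: a cycle "ends the day before the start of the next cycle", and the next one needs a dose. A patient pausing after Cycle 13 has no Cycle 14 until re-dosed.
- SAP 4.1.9: placement follows the recorded label, with no date window. No Cycle 14, 17, 20 or 23 Day 28 record therefore exists for that patient while off drug.

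**What happens to the absent record.** The documents give rules that do not agree. Protocol 9.4.2 counts a missing assessment that prevents evaluation as NR. SAP 4.4 bases percentages on patients with non-missing data. The Missing row in the response shells covers only patients with no post-baseline response assessment at all, which does not describe a patient on break.

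**Direction.** Let n be the patients at a time point, r the true responders and k the responders on break.

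- Counted as NR: (r − k)/n, which is k/n too low.
- Dropped: (r − k)/(n − k). The shortfall is r/n − (r − k)/(n − k) = k(n − r)/[n(n − k)], which is positive whenever r < n.

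Both rules bias the rate downward.

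**Size.** The plan states no figure to reproduce, and k is not given. Purely as an illustration, assume n = 20 and r = 10, a true rate of 50%:

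| k on break | Counted as NR | Dropped |
|---|---|---|
| 2 | 8/20 = 40% | 8/18 = 44% |
| 4 | 6/20 = 30% | 6/16 = 38% |
| 6 | 4/20 = 20% | 4/14 = 29% |

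A second assumed case uses r = 14 of 20 (70%), a responder count that Protocol 9.2.1 uses for Week 32. With k = 4 the rate prints as 10/20 = 50% or 10/16 = 62.5%.

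**Timing of break assessments.** Take a break starting at Week 52, and assume that the 84-day clock starts with the break (the protocol does not say). The 28-day hematology falls at Weeks 56, 60, 64, 68 and so on, and so meets Weeks 56, 68, 80 and 92 exactly. Full assessments fall at Weeks 64, 76, 88 and 100, which is 4 weeks before Weeks 68, 80, 92 and 104.

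**The case against.** The strongest reply is that SAP 4.1.9 says only what by-visit tables contain in general, and never excludes unscheduled records. It places assessments by recorded label, not by derived cycle. How sites label break visits depends on eCRF folders that are not shown, and the list of planned outputs is a separate document. Breaks are optional, may begin later than Cycle 13, and may be few. All analyses are descriptive, with no formal testing. These points stand as limits on certainty and size. They do not supply a mapping rule, and the protocol itself names the visits unscheduled.

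Three stronger readings are tempting, and the documents do not support them.

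- A reader might infer that dose delays create the same gap at Week 32, since footnote 19 to the schedule says that "performed assessment(s) would be recorded within the appropriate folder". But the main response table is headed for Week 32, CHR is defined at the Week 32 assessment, the schedule has one combined column for End of Cycle 8 and Week 32, and no shell prints a separate Cycle 8 Day 28 column.
- A reader might infer that duration of response is cut short. The only duration output shown in SAP 5.7.2.3 is the proportion lasting at least 12 weeks, from Week 32 to Cycle 11 Day 28 (Week 44). That ends before any break can start.
- A reader might infer that the best responders disappear. Hct control alone qualifies for a break, and not every qualifying patient will take one. The 75% and 40% Hct control rates in Protocol 9.2 are Week 32 planning scenarios, not forecasts of how many patients pause.

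**Conclusion.** The point holds for the descriptive by-visit rates of Hct control, CHR, ELN response and composite response from Cycle 14 Day 28 onward. As written, the rules leave responders on break without a scheduled record until treatment resumes, and either treatment of the absence lowers the rate. This goes beyond missing detail, because the stated rules produce an absence that depends on response.

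The conclusion assumes that break visits carry the unscheduled label the protocol gives them, that SAP 4.1.9 is applied literally, that at least one responder is on break, and that the true rate is below 100%. The size cannot be fixed from the documents. In the assumed 10-of-20 example the loss is 10 to 30 percentage points under the NR rule and about 6 to 21 points when patients are dropped, for 2 to 6 on break.

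The Week 32 primary and secondary endpoints and the durable-response proportion precede the earliest break and are not affected.

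**What to change.** In SAP 4.1.9, for response tables after Cycle 13, assign assessments by study day from first dose to nominal Weeks 56, 68, 80 and 92, and to Week 104 or the final visit, whatever the visit label. Include the unscheduled assessments made under Protocol 6.6.

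- Hct control and CHR: narrow windows. Plus or minus 14 days (half of 28) would capture one break hematology assessment each time.
- Spleen, ELN and composite: windows up to 84 days wide, because full assessments may fall between nominal weeks.
- Count patients on break by their assessed response.
- State one denominator rule for these tables, reconciling Protocol 9.4.2 with SAP 4.4. It should also cover a nominal time with no full assessment in its window. With windows of plus or minus 6 weeks, Week 56 spans Weeks 50 to 62, so a first full break assessment at Week 64 would count toward Week 68.
- Add a row for the number on break at each time point.

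The cost is SAP wording and the programming of two sets of windows, with no added visits or data. The drawbacks are that late time points mix patients on and off drug, which the added row shows, and that imaging-based responses may sit about 4 weeks from the nominal time.
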